#### **Monitoring and Oversight**

RBR samples will be tracked in a manner consistent with Good Clinical Practice by a quality-controlled, auditable, and appropriately validated laboratory information management system, to ensure compliance with data confidentiality as well as adherence to authorized use of samples as specified in this protocol and in the ICF. Sponsor monitors and auditors will have direct access to appropriate parts of records relating to an individual's participation in the RBR for the purposes of verifying the data provided to the Sponsor. The site will permit monitoring, audits, IRB/EC review, and health authority inspections by providing direct access to source data and documents related to the RBR samples.

### **9.              STATISTICAL CONSIDERATIONS**

#### **9.1              STATISTICAL HYPOTHESIS**

*Following the Sponsor's decision to phase out the study, no formal statistical hypothesis will be tested for this study.*

#### **9.2              ANALYSIS SETS**

The participant analysis sets for the purposes of analyses are defined in [Table 5](#).

**Table 5 Participant Analysis Sets**

| Participant Analysis Set | Description  |
|--------------------------|--|
| SAS                      | All participants exposed to study treatment; participants will be analyzed according to the treatment that they actually received. |

SAS=safety analysis set.

## 9.3 STATISTICAL ANALYSES

*As a result of the decision to phase out the study, no statistical analysis plan (SAP) will be provided for the study.*

### 9.3.1 General Considerations

All safety analyses will be performed on the SAS.

### 9.3.2 Estimation Methods for the Primary Endpoint

The *original* primary objective for this study *was* to evaluate the efficacy of tiragolumab plus atezolizumab compared with placebo plus atezolizumab in participants with resected, Stage IIB, IIIA, or select IIIB (T3N2 only) (AJCC 8th edition) [REDACTED] NSCLC who have received adjuvant platinum-based chemotherapy. The *original* primary endpoints *were* investigator-assessed DFS in the [REDACTED]. *After the Sponsor's decision to phase out the study, the primary objective for this study is to evaluate the single safety objective.*

#### 9.3.2.1 Safety Analyses

Safety analyses will be conducted in the SAS, defined as participants who receive at least one dose of tiragolumab/placebo or atezolizumab (see Section 9.2). Safety will be assessed through summaries of exposure to study treatment, adverse events, and changes in laboratory test results.

Study treatment exposure (such as treatment duration, total dose received, and number of cycles and dose modifications) will be summarized with descriptive statistics.

All verbatim adverse event terms will be mapped to MedDRA thesaurus terms, and adverse event severity will be graded according to NCI CTCAE v5.0. [REDACTED]

[REDACTED] All adverse events, serious adverse events, adverse events leading to death, adverse events of special interest, and adverse events leading to study treatment discontinuation that occur or worsen on or after the first dose of study treatment (i.e., treatment-emergent adverse events) will be summarized by mapped term, appropriate thesaurus level, and severity grade. For events of varying severity, the highest grade will be used in the summaries. Deaths and causes of death will be summarized.

Relevant laboratory, vital sign (pulse rate, respiratory rate, blood pressure, and temperature), and ECG data will be displayed by time, with grades identified where appropriate. Additionally, a shift table of selected laboratory tests will be used to summarize the baseline and maximum postbaseline severity grade. Changes in vital signs and ECGs will be summarized.

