**Table 2 Primary Objective and Corresponding Endpoint**

| Primary Objective  | Corresponding Endpoint  |
|---|--|
| 

To evaluate the safety of tiragolumab plus atezolizumab compared with placebo plus atezolizumab

 | 

Incidence and severity of adverse events, with severity determined according to NCI CTCAE v5.0

 |

NCI CTCAE v5.0 = National Cancer Institute Common Terminology Criteria for Adverse Events, Version 5.0.

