*Following the Sponsor's decision to phase out the study, patients in pre-screening or screening can be randomized and enrolled if they are eligible per the study inclusion criteria. An estimated [REDACTED] patients will be enrolled.*

[REDACTED] Eligible participants will be randomized in a 1:1 ratio to either the experimental arm (tiragolumab plus atezolizumab) or the comparator arm (placebo plus atezolizumab). Participants should receive their first dose of study treatment on the day of randomization if possible. [REDACTED]

Eligible participants will be stratified by tumor histology (squamous vs. non-squamous), disease stage (Stage IIB vs. Stage IIIA+ select IIIB [T3N2 only]) and PD-L1 status ([REDACTED]).

*As a result of the decision to phase out the study, the study will be unblinded. After participants have been unblinded and at the discretion of the investigator, participants randomized to the comparator arm may discontinue placebo and continue with atezolizumab monotherapy (1680 mg by IV infusion on Day 1 of each 28-day cycle) for a total of 13 cycles, approximately 1 year, in the absence of disease recurrence, or unacceptable toxicity. Participants randomized to the experimental arm, may at the discretion of the investigator, discontinue tiragolumab or continue to receive tiragolumab and atezolizumab (840 mg and 1680 mg respectively) by IV [REDACTED] on*

*Day 1 of each 28-day cycle for a total of 13 cycles, approximately 1 year, in the absence of disease recurrence, or unacceptable toxicity.*

Crossover from the *comparator* arm to the *experimental* arm will not be allowed.

All participants will undergo scheduled disease assessment scans by computed tomography (CT) at screening *and per local standard practice during the study treatment period*. Disease assessments will continue *per local standard practice* until disease recurrence, withdrawal of consent, death, or study termination by the Sponsor, whichever occurs first.

Safety assessments will include the incidence, nature, and severity of adverse events, graded per National Cancer Institute Common Terminology Criteria for Adverse Events (NCI CTCAE) Version 5.0.

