### **6.3.2      Blinding**

*Originally*, study site personnel and participants will be blinded to treatment assignment during the study. The Sponsor and its agents will also be blinded to treatment assignment, with the exception of individuals who require access to participant treatment assignments to fulfill their job roles during a clinical trial.

*After the Sponsor's decision to phase out the study, the Sponsor and its agents, study site personnel, and participants will be unblinded to treatment assignment.*

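### The adverse event summary has no separation at unblinding, so the tiragolumab-versus-placebo comparison can mix blinded data with open-label reporting and time off tiragolumab

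*Combined protocol and SAP*

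**What the plan says.** The sole objective is comparative (Section 3, Table 2): "To evaluate the safety of tiragolumab plus atezolizumab compared with placebo plus atezolizumab". Its endpoint is "Incidence and severity of adverse events, with severity determined according to NCI CTCAE v5.0".

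On the analysis, Section 9.3.2.1 sets one window. Adverse events "that occur or worsen on or after the first dose of study treatment (i.e., treatment-emergent adverse events) will be summarized by mapped term", and "For events of varying severity, the highest grade will be used in the summaries". Section 9.2 (Table 5) groups participants by the treatment actually received. It gives no rule for someone whose treatment changes part-way. Section 9.3 states that there will be no SAP, and Section 9.1 that no hypothesis will be tested.

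On conduct, Section 6.3.2 says that after the phase-out decision "the Sponsor and its agents, study site personnel, and participants will be unblinded to treatment assignment". Under Section 4.1, "participants randomized to the comparator arm may discontinue placebo and continue with atezolizumab monotherapy", while participants in the experimental arm may, at the investigator's discretion, "discontinue tiragolumab or continue to receive tiragolumab and atezolizumab". The same section adds: "Crossover from the *comparator* arm to the *experimental* arm will not be allowed". Section 6.1 repeats the two permissions.

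**The concern.** Before unblinding, the arms are randomized, masked and on their assigned drugs. After it, two things can change, and they pull in opposite directions.

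- **Reporting.** Participants and investigators know who receives tiragolumab when they notice, report and grade events. Section 2.2.2 attributes the Phase II imbalance in immune-mediated events mainly to rash and infusion-related reactions, and Section 2.3 describes it as mostly Grade 1 and 2. Expected, low-grade events are the kind most open to differential reporting.
- **Contrast.** An experimental-arm participant who stops tiragolumab is on atezolizumab alone, as the comparator arm is in active drug. Later events in that participant still count in one cell with the earlier ones.

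Because the highest grade over the whole window is used, an open-label grade can replace a blinded one for the same event. A reader of the pooled table could not tell how much of a difference, or of its absence, comes from the masked period. No SAP is planned that would add the separation later.

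**Working it through.** The plan gives no effect size, power or event rate for this endpoint, so there is no figure of its own to reproduce. What follows is an illustration of scale.

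**Inputs from the documents**
- Immune-mediated events in the Phase II trial: 69% vs 47%; immune-mediated rash: 40% vs 15% (Section 2.2.2).
- About 60 participants (Synopsis), randomized 1:1 (Section 4.1), so about 30 per arm.
- Treatment course: 13 cycles × 28 days = 364 days (Section 4.1).

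**Assumptions, not in the documents**
- The Phase II percentages, from advanced disease, are treated as one-course risks with constant hazards.
- u = share of the course before unblinding, 0.25 to 0.75.
- s = share of the experimental arm that stops tiragolumab at unblinding, 0 to 1. Those who stop take the comparator hazard.
- r = reporting multiplier after unblinding for those who stay on tiragolumab, 1 to 1.5.

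**Formulas**
- Course hazard h = −ln(1 − p). Immune-mediated: hT = −ln(0.31) = 1.171 and hC = −ln(0.53) = 0.635.
- Stay: 1 − exp(−[u·hT + (1−u)·r·hT]). Stop: 1 − exp(−[u·hT + (1−u)·hC]).
- Pooled difference = (1−s)·stay + s·stop − pC.

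**Immune-mediated events, u = 0.5 (22.0 points with neither effect)**
- Stop: 1 − exp(−[0.586 + 0.317]) = 59.5%.
- Stay, r = 1.5: 1 − exp(−[0.586 + 0.878]) = 76.9%.

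| s | r | Pooled difference (points) |
|---|---|---|
| 0.25 | 1 | 19.6 |
| 0.5 | 1 | 17.2 |
| 1 | 1 | 12.5 |
| 0 | 1.25 | 26.2 |
| 0 | 1.5 | 29.9 |
| 0.5 | 1.5 | 21.2 |

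The last row nearly returns the 22.0, so the two effects can hide each other. Over the grid the range is 6.7 to 33.0 at u = 0.25 and 17.6 to 26.2 at u = 0.75. For rash (25.0 points) it is 13.6 to 32.2 at u = 0.5.

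**Sampling error at 30 per arm**
- 1.96·√(0.69·0.31/30 + 0.47·0.53/30) = 24.3 points; for rash, 21.7 points.

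**What a blinded-only table would show**
- At u = 0.5: 44.3% vs 27.2%, 17.1 points for immune-mediated events; 14.7 points for rash.
- At u = 0.25: 25.4% vs 14.7%, 10.7 points for immune-mediated events.
- These are smaller only because the window is shorter, which is why raw percentages by period are not enough.

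**Second illustration, all inputs assumed** (comparator 0.06 per month, rate ratio 1.5, 12 months, unblinding at month 4)
- Comparator: 1 − exp(−0.72) = 51.3%. Always on tiragolumab: 1 − exp(−1.08) = 66.0%. Difference 14.7 points.
- Stop at month 4: 1 − exp(−[0.36 + 0.48]) = 56.8%. If half stop, the arm shows (66.0 + 56.8)/2 = 61.4% and the difference is 10.1, a shift of 4.6 points.
- No true effect but 25% more reporting after unblinding: 1 − exp(−[0.24 + 0.60]) = 56.8% vs 51.3%, a false excess of 5.5 points.
- Half-width for 61.4% vs 51.3%: about 25 points.
- Blinded window only: 30.2% vs 21.3%, 8.9 points over 4 of 12 months, half-width about 22.

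**The case against.** The strongest reply is that this is a descriptive close-out. Nothing is tested, about 60 participants are enrolled, and Section 4.1 now puts the purpose as treatment continuity and safety for those still treated. Counting every event from first dose is a legitimate description of the full course. Sampling error of 24 to 25 points exceeds the 4.6- and 5.5-point shifts in the second illustration and most of those in the first. All of this stands, and it limits the weight of the point. It does not remove it, because Table 2 still states the objective as a comparison.

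A second reply is that a blinded-period table should not displace the full one. That also stands. It covers a shorter window that may differ between participants, has fewer events and says little about late onset. In the second illustration its 8.9 points against a half-width of 22 is no more precise than 10.1 against 25.

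Third, part of the need is met. Section 6.4 places dose and timing on the Study Drug Administration eCRF, and Section 9.3.2.1 summarizes exposure, so a split remains possible at reporting. But possible is not planned, and no visible text calls for recording unblinding dates.

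Fourth, any-grade adverse events were near ceiling in Phase II (98.5% vs 97.1%, Section 2.2.2), so that line can hardly move. The exposed lines are specific terms and grades.

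Fifth, redacted text sits directly before the sentence at issue. It could hold a relevant rule, so confidence is moderate. The visible sentence still sets a single window.

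**Conclusion.** The point holds as an inexpensive improvement to interpretation. The visible plan pools blinded and open-label events, including those arising after tiragolumab has been stopped, in the summary of the only endpoint. Unblinding dates and stopping rates are not given, so the size and net direction of any bias cannot be determined. The illustrated range of 6.7 to 33.0 points around 22.0 rests on the assumed u, s and r.

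Four stronger readings may tempt a reader, and the documents do not support them:
- *The pooled table will overstate tiragolumab's toxicity.* Dilution works the other way and can cancel the reporting effect.
- *Stopping placebo also erodes the contrast.* It changes no active drug, and crossover to tiragolumab is barred. Only stopping tiragolumab matters.
- *Unblinded causality judgments bias the endpoint.* The endpoint is incidence and severity, and Appendix 3 (A3–1) counts events whether or not they are considered related.
- *The trial's inference is compromised unless the blinded table replaces the full one.* No test or type I error is at stake, and the full-course table has its own use.

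**What to change.** In Section 9.3.2.1, keep the full-period table and add:

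1. An adverse event summary by randomized arm, split at each participant's unblinding date: onset or worsening before it, and on or after it. Apply the highest-grade rule within each period.
2. Person-time at risk, or exposure-adjusted rates, for each arm and period.
3. A sentence saying that the tiragolumab-versus-placebo comparison is read primarily from the blinded period.
4. A rule, consistent with Table 5, that participants who drop tiragolumab stay in the tiragolumab group.

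Record the unblinding date for each participant; the documents do not say that the IxRS holds it. Derive the last tiragolumab/placebo dose date from the Study Drug Administration eCRF (Section 6.4).

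The cost is a few sentences, one recorded date per participant and one extra set of tables. The downside is a shorter blinded window with fewer events and less information on late-onset events, which is the reason to retain the full-period table. The change concerns analysis and recording only and leaves the treatment options in Sections 4.1 and 6.1 as they are.

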### **9.3.3            Other Analyses**

#### **9.3.3.1        Summaries of Conduct of Study**

Enrollment, study treatment administration, and discontinuation from the study will be summarized by treatment arm. The reasons for study treatment discontinuation will also be tabulated. Major protocol deviations, including major deviations with regard to the inclusion and exclusion criteria, will be *provided* by treatment arm.

#### **9.3.3.2        Summaries of Demographics and Baseline Characteristics**

Demographics and baseline characteristics (including age, sex, race/ethnicity) will be summarized by treatment arm. Baseline data are the last data obtained prior to initiation of study treatment. Descriptive statistics (mean, standard deviation, median, and range) will be presented for continuous variables and counts and percentages will be presented for categorical variables.

**A1–1      REGULATORY AND ETHICAL CONSIDERATIONS**

This study will be conducted in accordance with the protocol and with the following:

- Consensus ethical principles derived from international guidelines, including the Declaration of Helsinki and Council for International Organizations of Medical Sciences international ethical guidelines
- Applicable International Council for Harmonisation (ICH) E6 guideline for Good Clinical Practice
- Applicable laws and regulations.

The protocol, Informed Consent Form, Investigator's Brochure, and other relevant documents (e.g., advertisements) must be submitted to an Institutional Review Board (IRB)/Ethics Committee (EC) by the investigator and reviewed and approved by the IRB/EC before the study is initiated.

Any substantial amendments to the protocol will require IRB/EC and health authority approval (as locally required) before implementation of changes, with the exception of administrative changes or changes necessary to eliminate an immediate hazard to study participants.

The investigator will be responsible for the following:

- Providing written summaries of the status of the study to the IRB/EC annually or more frequently in accordance with the requirements, policies, and procedures established by the IRB/EC
- Notifying the IRB/EC of serious adverse events or other significant safety findings, as required by IRB/EC procedures
- Providing oversight of the conduct of the study at the site and ensuring adherence to requirements of 21 Code of Federal Regulations (CFR) (U.S. sites only), the ICH Guideline for Good Clinical Practice, the IRB/EC, Clinical Trials Directive (2001/20/EC) or Clinical Trials Regulation (536/2014) (EEA sites only), and all other applicable local regulations

**A1–2      FINANCIAL DISCLOSURE**

Investigators will provide the Sponsor with sufficient, accurate financial information in accordance with local regulations to allow the Sponsor to submit complete and accurate financial certification or disclosure statements to the appropriate health authorities. Investigators are responsible for providing information on financial interests during the study and for 1 year after completion of the study (see definition of end of study in Section 4.4).

### **A1–3      INFORMED CONSENT PROCESS**

The investigator or authorized designee will explain the nature of the study, including the risks and benefits, to the participant or their legally authorized representative and answer all questions regarding the study.

Participants must be informed that their participation is voluntary. Participants or their legally authorized representative will be required to sign a statement of informed consent that meets the requirements of 21 CFR 50 (U.S. sites only), the ICH Guideline for Good Clinical Practice, and the IRB/EC.

The medical record must include a statement that written informed consent was obtained before the participant was enrolled in the study and the date the written consent was obtained. The authorized person obtaining the informed consent must also sign the Informed Consent Form.

If the Informed Consent Form is revised (through an amendment or an addendum) to communicate information that might affect a participant's willingness to continue in the study, the participant or their legally authorized representative must re-consent by signing the most current version of the Informed Consent Form or the addendum, in accordance with applicable laws and IRB/EC policy.

A copy of each Informed Consent Form must be provided to the participant or their legally authorized representative.

### **A1–4      DATA PROTECTION**

Information technology systems used to collect, process, and store study-related data are secured by technical and organizational security measures designed to protect such data against accidental or unlawful loss, alteration, or unauthorized disclosure or access. In the event of a data security breach, appropriate mitigation measures will be implemented.

Participants will be assigned a unique identifier by the Sponsor. Any participant records or datasets that are transferred to the Sponsor will contain the identifier only; the participant's name or any information that would make the participant identifiable will not be transferred.

Participants must be informed that their personal study-related data will be used by the Sponsor in accordance with local data protection law. The level of disclosure must also be explained to participants, who will be required to give consent for their data to be used as described in the Informed Consent Form.

## **Appendix 1: Regulatory, Ethical, and Study Oversight Considerations**

---

Participants must be informed that their medical records may be examined by auditors or other authorized individuals representing the Sponsor or Sponsor collaborators and licensees, by appropriate IRB/EC members, and by inspectors from health authorities.

### **A1–5      ADMINISTRATIVE STRUCTURE**

This trial will be sponsored and managed by F. Hoffmann-La Roche Ltd. The Sponsor will provide clinical operations management, data management, and medical monitoring.

Approximately 400 sites globally will participate to enroll approximately 1150 participants. Enrollment will occur through an interactive voice or web-based response system.

Central facilities will be used for certain assessments throughout the study (e.g., biomarker analyses), as specified in Section 8. Accredited local laboratories will be used for routine monitoring; local laboratory ranges will be collected.

### **A1–6      DISSEMINATION OF CLINICAL STUDY DATA**

Study data may be submitted to government or other health research databases or shared with researchers, government agencies, companies, or other groups that are not participating in this study. These data may be combined with or linked to other data and used for research purposes, to advance science and public health, or for analysis, development, and commercialization of products to treat and diagnose disease. In addition, redacted Clinical Study Reports and/or other summaries of clinical study results may be available in health authority databases for public access, as required by local regulation, and will be provided upon request. For more information, refer to the Roche Global Policy on Sharing of Clinical Study Information at the following website:

<https://www.roche.com/innovation/process/clinical-trials/data-sharing/>

Given the complexity and exploratory nature of exploratory biomarker analyses, data derived from these analyses will generally not be provided to study investigators or participants unless required by law (with the exception of the report from Foundation Medicine). The aggregate results of any conducted research will be available in accordance with the effective Roche policy on study data publication.

